4.2.5 Maintenance Phase Day 1 (Visit 6)

The Maintenance Phase Day 1 will take place on the day the subject achieves an i-STAT potassium value between 3.5 and 5.0 mmol/L, inclusive, after 24 (Visit 3), 48 (Visit 4), or 72 hours (Visit 5) of ZS 10 g TID treatment during the Correction Phase and procedures listed below should take place immediately after procedures of visit 3, 4 or 5, as applicable.

The following assessments will be performed:

- Clinical chemistry will be performed (Sample will be the same sample as obtained on the last day of the Correction Phase).
- An ECG will be performed (Section 5.2.3).
- Obtain vital signs (pulse rate and blood pressure) (Section 5.2.4).
- A targeted physical examination including weight (Section 5.2.2).
- The clinic staff access the IVRS/IWRS to record that the subject entered the Maintenance Phase. The system will assign the subject a new Maintenance Phase investigational product kit containing an additional supply of ZS.
- The first dose of ZS during the Maintenance Phase will be administered in the clinic as a suspension in water. The clinic staff will solicit any adverse events.
- Subjects will be sent home. They will be requested to fill out a dosing schedule card indicating when they took ZS. Subjects will return to the clinic on Maintenance Phase Day 2 and bring the used investigational product boxes and sachets and dosing schedule card with them.

4.2.6 Maintenance Phase Day 2 (Visit 7)

- Subjects will arrive at the clinic in the morning, fasting for at least 8 hours prior to potassium sample collection. Subjects need to bring kit previously dispensed at Maintenance Phase Day 1.
- The clinic staff will solicit any adverse events, note any changes in concomitant medications, note if the subject has visited a doctor or emergency room since the last visit, examine the returned investigational product sachets and make note of when the doses were taken and any unused investigational products on the eCRF and source documents.
- An ECG will be performed (Section 5.2.3).
- Prior to ZS administration, potassium samples (i-STAT and Central Laboratory) will be collected. If the i-STAT value is > 5.0 mmol/L or between 3.0 and 3.4 mmol/L while receiving 5 g QD, a second potassium measurement (i-STAT and Central Laboratory) will be obtained 10 (± 2) minutes later. If both i-STAT values are as stated above, the dose will be adjusted in accordance with Section 7.2, Table 6.
- The ZS dose will be administered in the clinic as a suspension in water.
- Subjects will be sent home. They will be requested to fill out a dosing schedule card indicating when they took ZS. Subjects will return to the clinic for the next scheduled visit and bring the used investigational product boxes and sachets and dosing schedule card with them.

4.2.7 Maintenance Phase Day 5 (Visit 8)

- Subjects will arrive at the clinic in the morning, fasting for at least 8 hours prior to potassium sample collection. Subjects need to bring kit previously dispensed at Maintenance Phase Day 1.
- The clinic staff will solicit any adverse events, note any changes in concomitant medications, note if the subject has visited a doctor or emergency room since the last visit, examine the returned investigational product sachets and make note of when the doses were taken and any unused investigational products on the eCRF and source documents.
- An ECG will be performed (Section 5.2.3).
- Blood samples for the assessment of hematology will be collected.
- Prior to ZS administration, blood samples for i-STAT potassium and assessment of clinical chemistry including S-K will be collected. If the i-STAT value is > 5.0 mmol/L while receiving 5 g QD, 5 g QOD (or 2.5 g QD), 10 g QD or 15 g QD or between 3.0 and 3.4 mmol/L, inclusive, a second potassium measurement (i-STAT and Central Laboratory) will be obtained 10 (\pm 2) minutes later. If both i-STAT values are as stated above, the dose will be adjusted in accordance with Section 7.2, Table 6.
- The ZS dose will be administered in the clinic as a suspension in water.
- Subjects will be sent home. They will be requested to fill out a dosing schedule card indicating when they took ZS. Subjects will return to the clinic for the next scheduled visit and bring the used investigational product boxes and sachets and dosing schedule card with them.

4.2.8 Maintenance Phase Day 12 (Visit 9)

- Subjects will arrive at the clinic in the morning, fasting for at least 8 hours prior to potassium sample collection.
- The clinic staff will solicit any adverse events, note any changes in concomitant medications, note if the subject has visited a doctor or emergency room since the last visit, examine the returned investigational product boxes and sachets and make note of when the doses were taken and any unused investigational products on the eCRF and source documents.
- An ECG will be performed (Section 5.2.3).
- Obtain vital signs (pulse rate and blood pressure) (Section 5.2.4).
- A targeted physical examination including weight (Section 5.2.2).
- Blood samples for the assessment of hematology will be collected.
- Prior to ZS administration, blood samples for i-STAT potassium and assessment of clinical chemistry including S-K will be collected. If the i-STAT value is > 5.0 mmol/L while receiving 5 g QD, 5 g QOD (or 2.5 g QD), 10 g QD or 15 g QD or

between 3.0 and 3.4 mmol/L, inclusive, a second potassium measurement (i-STAT and Central Laboratory) will be obtained 10 (\pm 2) minutes later. If both i-STAT values are as stated above, the dose will be adjusted in accordance with Section 7.2, Table 6.

- The clinic staff will access the IVRS/IWRS and provide the 7-digit subject identification number and the i-STAT potassium value. The system will assign the subject a new Maintenance Phase investigational product kit containing an additional supply of ZS.
- The ZS dose will be administered in the clinic as a suspension in water.
- Subjects will be sent home with the investigational product kit and instructions on how to take ZS. They will be requested to fill out a dosing schedule card indicating when they took ZS. Subjects will return to the clinic for the next scheduled visit and bring the used investigational product boxes and sachets and dosing schedule card with them.

4.2.9 Maintenance Phase Day 19 (Visit 10)

- Subjects will arrive at the clinic in the morning, fasting for at least 8 hours prior to potassium sample collection. Subjects need to bring kit previously dispensed at Maintenance Phase Day 12.
- The clinic staff will solicit any adverse events, note any changes in concomitant medications, note if the subject has visited a doctor or emergency room since the last visit, examine the returned investigational product sachets and make note of when the doses were taken and any unused investigational products on the eCRF and source documents.
- An ECG will be performed (Section 5.2.3).
- Obtain vital signs (pulse rate and blood pressure) (Section 5.2.4).
- Blood samples for the assessment of hematology will be collected.
- Prior to ZS administration, blood samples for i-STAT potassium and assessment of clinical chemistry including S-K will be collected. If the i-STAT value is $>$ 5.0 mmol/L while receiving 5 g QD, 5 g QOD (or 2.5 g QD), 10 g QD or 15 g QD or between 3.0 and 3.4 mmol/L, inclusive, a second potassium measurement (i-STAT and Central Laboratory) will be obtained 10 (\pm 2) minutes later. If both i-STAT values are as stated above, the dose will be adjusted in accordance with Section 7.2, Table 6.
- The ZS dose will be administered in the clinic as a suspension in water.
- Subjects will be sent home. They will be requested to fill out a dosing schedule card indicating when they took ZS. Subjects will return to the clinic for the next scheduled visit and bring the used investigational product boxes and sachets and dosing schedule card with them.

4.2.10 Maintenance Phase Day 26- Day 334 (Visit 11- Visit 22)

- Subjects will arrive at the clinic in the morning, fasting for at least 8 hours prior to potassium sample collection.
- The clinic staff will solicit any adverse events, note any changes in concomitant medications, note if the subject has visited a doctor or emergency room since the last visit, examine the returned investigational product boxes and sachets and make note of when the doses were taken and any unused investigational products on the eCRF and source documents.
- Prior to ZS administration, potassium samples (i-STAT and Central Laboratory) will be collected. S-K will be evaluated as part of the clinical chemistry sample on Visits 11, 13, 16, 19 and 22. If the i-STAT value is > 5.0 mmol/L while receiving 5 g QD, 5 g QOD (or 2.5 g QD), 10 g QD or 15 g QD or between 3.0 and 3.4 mmol/L, inclusive, a second potassium measurement (i-STAT and Central Laboratory) will be obtained 10 (± 2) minutes later. If both i-STAT values are as stated above, the dose will be adjusted in accordance with Section 7.2, Table 6.
- Samples will be collected prior to any IP administration.
 - Blood samples for assessment of hematology and clinical chemistry including S-K (Visits 11, 13, 16, 19 and 22).
 - Aldosterone and renin collected prior to 10 am (1000) after the subject has been in an upright position for at least 2 hours and before recording the ECG and physical examination (Visits 16).
 - Urine for urinalysis parameters (Visits 11, 13, 16, 19 and 22).
- An ECG will be performed (Section 5.2.3) (Visits 11, 12, 13, 16, 19 and 22).
- Obtain vital signs (pulse rate and blood pressure) (Section 5.2.4).
- A targeted physical examination including weight (Section 5.2.2).
- The site will access the IVRS/IWRS and provide the 7-digit subject identification number and the i-STAT potassium value. The system will assign the subject a new Maintenance Phase investigational product kit containing an additional supply of ZS.
- The ZS dose will be administered in the clinic as a suspension in water.
- Subjects will be sent home with the investigational product kit and instructions on how to take ZS. They will be requested to fill out a dosing schedule card indicating when they took ZS. Subjects will return to the clinic for the next scheduled visit and bring the used investigational product boxes and sachets and dosing schedule card with them.

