3.9 Discontinuation of investigational product

Patients may be discontinued from investigational product (IP) in the following situations:

- Patient decision. The patient is at any time free to discontinue treatment, without prejudice to further treatment
- Adverse Event
- Severe non-compliance with the Clinical Study Protocol
- Risk to patient as judged by investigator
- Pregnancy
- Require treatment with medications prohibited or contraindicated for use due to safety concerns with ZS
- Patient develops potassium values which meet the IP discontinuation criteria described in [Table 6](#) (confirmed by taking a second potassium measurement after a 10 ± 2 -minute interval, and both i-STAT values meet the study drug discontinuation rule). Patients discontinuing due to this criterion must immediately receive appropriate medical treatment to manage their hypo- or hyperkalemia.

Patient develops clinically significant cardiac condition (see below). The patient should immediately receive appropriate medical treatment and be discontinued from study drug.

- Serious cardiac arrhythmias (ventricular tachycardia or ventricular fibrillation, new atrial fibrillation or atrial flutter, new paroxysmal supraventricular tachycardia [other than sinus tachycardia], new 2nd or 3rd degree AV block or significant bradycardia [HR < 40 bpm])
- Acute heart failure
- Significant increase in PR interval (> 250 msec in the absence of pre-existing atrioventricular block) or widening of the QRS complex (>140 msec in the absence of pre-existing bundle branch block). If an ECG shows peaked T-wave, the serum potassium must be checked immediately and decide whether to continue the IP based on the criteria described in [Section 3.9](#).
- An absolute QTc >550msec, or an increase in QTc interval > 60msec from baseline to more than 500msec. All patients meeting the QTc>500ms criterion should immediately have potassium assessed by i-STAT and central lab, if not already done within 1 hour of the collection of the ECG

Patients who discontinue from study medication during the Correction Phase conduct Visit5 procedure soon after the discontinuation and conduct EOS Visit one week after last IP.

Patients who discontinue from study medication during the Maintenance Phase conduct Visit23 procedure soon after the discontinuation and conduct EOS Visit one week after last IP.

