3.11 Interruption of investigational product

Investigational product (IP) may be interrupted in situations such as an adverse event, laboratory abnormality other than potassium abnormality (only during Maintenance Phase) at the investigator's discretion.

During an interruption of IP, the patient will return to the site at least every 7 (\pm 2) days as an extra visit for a potassium measurement and recording of any adverse events and concomitant medications (Patient will arrive at the clinic in the morning after fasting for at least 8 hours prior to potassium sample collection.). In case it is unlikely to re-start IP, patient should be discontinued from the IP. On each extra visit, investigator and sponsor should discuss the study continuation. When the patient re-start IP, dose should be the same as the last dose before interruption. If the IP was interrupted due to an AE, the causality of the AE must be judged by investigator to be not related to IP upon resuming the IP.

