6.3.6 Adverse events based on examinations and tests

The results from the Clinical Study Protocol mandated laboratory tests and vital signs will be summarised in the Clinical Study Report (CSR). Deterioration as compared to baseline in protocol-mandated laboratory values, vital signs should therefore only be reported as AEs if they fulfil any of the SAE criteria or are the reason for discontinuation of treatment with the investigational product.

If deterioration in a laboratory value/vital sign is associated with clinical signs and symptoms, the sign or symptom will be reported as an AE and the associated laboratory result/vital sign will be considered as additional information. Wherever possible the reporting Investigator uses the clinical, rather than the laboratory term (e.g., anaemia versus low haemoglobin value). In the absence of clinical signs or symptoms, clinically relevant deteriorations in non-mandated parameters should be reported as AE(s).

Any new or aggravated clinically relevant abnormal medical finding at a physical examination as compared with the baseline assessment will be reported as an AE.

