If a patient develops i-STAT potassium values between 3.0 mmol/L and 3.4 mmol/L, inclusive (confirmed by taking a second potassium measurement after a 10 ± 2 minute interval) during the Correction Phase the subject will be directed to not take any more study drug for the remainder of the day and return the next day to continue in the study. E.g. Patients with potassium values between 3.0 mmol/L and 3.4 mmol/L on Day 2 will not take the drug the rest of the doses on Day 2, and will return fasting to have their potassium tested again on Day 3 and continue their therapy. If the potassium has normalized, the patients will start Maintenance Phase from the day. If patients with potassium values between 3.0 mmol/L and 3.4 mmol/L on Day 3, the patients will not take the drug the rest of the doses on Day 3, and will return fasting to be assessed for entering into the Maintenance Phase on Day 4.

Patients with i-STAT potassium <3.0 mmol/L (confirmed by taking a second potassium measurement after a 10 ± 2 minute interval) should discontinue from therapy.

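### At 5, 10 or 15 g QD in the Maintenance Phase, a repeat i-STAT pair with one value ≤2.9 and one 3.0–3.4 mmol/L has no mandated step-down or stop (minor)

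*Protocol*

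**What the plan says.** Sections 4.2.7–4.2.10 (Visits 8–22) call for a repeat reading after about 10 minutes when the first i-STAT value is above 5.0 or "between 3.0 and 3.4 mmol/L, inclusive, a second potassium measurement (i-STAT and Central Laboratory) will be obtained". Section 4.2.6 (Visit 7) has the same band for the only dose then in use: "or between 3.0 and 3.4 mmol/L while receiving 5 g QD". Each section makes the dose change conditional on the pair: "If both i-STAT values are as stated above, the dose will be adjusted in accordance with Section 7.2, Table 6".

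Section 3.9 governs stopping for potassium and also looks at the pair. It applies when "both i-STAT values meet the study drug discontinuation rule".

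Table 6 in Section 7.2 is indexed to a single value. At 5, 10 and 15 g QD, ≤2.9 means stop, 3.0–3.4 means one step down, and no change begins at 3.5. At 5 g QOD or 2.5 g QD both low bands mean stop. Section 7.2 also requires an extra visit 7 (±2) days after any ZS dose adjustment.

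**The concern.** The step-down rule needs two values inside one row of Table 6, and the stop rule needs two values inside the row below it. Neither covers a pair that falls across the boundary between 2.9 and 3.0. Read as written, the protocol then demands less for a lower pair than for a milder one, which cannot be intended.

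The recheck is also at stake. It depends on a dose adjustment, so a patient with both readings below 3.5 could receive the usual dose in the clinic and go home until the next scheduled visit. Hypokalemia is a named safety endpoint in Section 8.5.2, and the study's primary objective is safety. With about 30 centers, sites left to improvise may also differ, some stepping down and others stopping.

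**Working it through.** **Pair rules at 5, 10 and 15 g QD**

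| Repeat pair (mmol/L) | Both in 3.0–3.4 (4.2.6–4.2.10)? | Both ≤2.9 (3.9 with Table 6)? | Mandated action |
|---|---|---|---|
| 3.3 and 3.4 | yes | no | one step down, recheck at 7 (±2) days |
| 2.9 and 3.0 | no | no | none |
| 2.8 and 2.9 | no | yes | stop |

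**Counting the combinations.** Take values from 2.5 to 3.4 in steps of 0.1: five are ≤2.9 and five are 3.0–3.4, giving 10 × 10 = 100 ordered pairs.
- Both 3.0–3.4: 5 × 5 = 25, step down.
- Both ≤2.9: 5 × 5 = 25, stop.
- One of each: 2 × 5 × 5 = 50, neither condition met.
- At 5 g QOD or 2.5 g QD: 0 uncovered, because both bands say stop.

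Readings taken ten minutes apart should be close, so the near pairs are more relevant:
- Difference at most 0.1: 10 + 2 × 9 = 28 ordered pairs, of which 2 straddle the boundary.
- Difference at most 0.2: 28 + 2 × 8 = 44 ordered pairs, of which 6 straddle it.

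These are counts of combinations on a chosen grid, not frequencies. The protocol gives no basis for a frequency among the 150 patients.

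**Time to the next required potassium** (days from Table 2; windows from its footnote 5)
- Visit 7 to 8: 5 − 2 = 3 days. Visits 8 to 9, 9 to 10 and 10 to 11: 7 days each.
- Visit 11 to 12 through Visit 22 to 23: 28 days each, for example 54 − 26 = 28 and 362 − 334 = 28. This is 12 of the 16 titration visits (Visits 7–22).
- With ±3 days at each end: 28 ± 6 = 22 to 34 days.
- After a step-down: 7 ± 2 = 5 to 9 days.
- Delay: 28 − 7 = 21 days nominal, from 22 − 9 = 13 to 34 − 5 = 29 days with windows.

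After Visits 7–10 the next scheduled visit is 3–7 days away, so only the missing dose instruction remains.

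**Where the gap comes from.** Table 6 has an action for every value below 3.5, so the table is complete. The high-side trigger is open-ended (above 5.0), so a pair such as 6.4 and 6.6 still satisfies the visit-section condition, and 3.9 does not stop dosing because only one value exceeds 6.5. The low trigger alone is closed at its lower end.

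**The case against.** The strongest reply is that Table 6 governs dosing and gives no-change only from 3.5 upward. Whichever value of a mixed pair is used, the table says reduce or stop, so the doubt is only about which. At Visit 9 and Visits 11–22 the site also enters one i-STAT value in the IVRS/IWRS before a kit is assigned, and neither value of such a pair corresponds to no change. This makes an unchanged dose unlikely in practice. However, the visit sections state a condition on both values before Table 6 is applied, and the protocol does not say that the system applies the table.

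A second reply is that 3.2 followed by 2.8 yields a new value in the stopping row, which would need its own confirmation. That reading is reasonable, but no third sample is written. It would reach only the 25 of the 50 mixed pairs in which the low value comes second.

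Discretionary routes also exist. Section 3.9 permits stopping for "Risk to patient as judged by investigator". Section 3.11 permits interruption "in situations such as an adverse event, laboratory abnormality other than potassium abnormality", so low potassium alone does not open it, but symptoms can, because under 6.3.6 "the sign or symptom will be reported as an AE". Section 5.2.1 allows extra samples, and a change of diuretic or RAAS inhibitor dose brings a visit at 7 (±2) days under 7.7. These routes reduce the risk, but none requires the step-down.

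The 7.2 sentence beginning "Patients with i-STAT potassium <3.0 mmol/L (confirmed by taking a second potassium measurement" does not close the gap, since it too asks for confirmation. From its place in the Synopsis it is probably a Correction Phase rule, and nothing here rests on it.

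**Conclusion.** The point holds as a minor correction to a safety rule. It affects three of the four dose rows of Table 6 (only the 5 g QD row at Visit 7). In the worst case the next required potassium comes 21 days later than after a step-down (13–29 with windows), following 12 of 16 titration visits.

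This rests on a literal reading of the two pair conditions, on two samples ending the confirmation, and, for the delay, on no discretionary route being used. Such pairs are probably uncommon, and most investigators would act on them anyway. Sample size and analysis are unaffected. The Correction Phase is outside this point.

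**What to change.** In 4.2.6–4.2.10, replace the low trigger of 3.0–3.4 with <3.5 mmol/L and add: *If both i-STAT values are ≤2.9 mmol/L, discontinue dosing (Section 3.9); otherwise, if both are <3.5 mmol/L, apply the 3.0–3.4 row of Table 6.*

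On the 100-pair grid this sends 75 pairs to the 3.0–3.4 row and 25 to stop, with none unassigned and none given two instructions. Section 3.9 and Table 6 stay as they are, and nothing changes at 5 g QOD or 2.5 g QD. Step-down is proposed for the mixed pair because 3.9 already reserves stopping for two values in the stopping row. If the sponsor prefers that the lower value govern, which is defensible for a pair such as 2.5 and 3.0, then 3.9 must change as well.

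The cost is a short amendment repeating the same text in five sections, plus a site memo. Each patient newly stepped down has one extra visit of a type already defined in 7.2, with one potassium sample (4.5 mL in Table 5). The repeat sample after a first value ≤2.9 is already required by 3.9.

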4.2.11 Maintenance Phase Day 362 (Visit 23)

- Subjects will arrive at the clinic in the morning, fasting for at least 8 hours prior to potassium sample collection.
- Administer the SF-36 v2 questionnaire. The patient should complete the questionnaire prior to any other study procedures.
- Enter the patient questionnaire in patients who were prescribed ZS 5 g QOD.
- The clinic staff will solicit any adverse events, note any changes in concomitant medications, note if the subject has visited a doctor or emergency room since the last visit, examine the returned investigational product boxes and sachets and make note of when the doses were taken and any unused investigational products on the eCRF and source documents.
- Blood samples for i-STAT potassium and assessment of hematology and clinical chemistry including S-K will be collected.
- Aldosterone and renin collected prior to 10 am (1000) after the subject has been in an upright position for at least 2 hours and before recording the ECG and physical examination.
- Assessment of urinalysis parameters.
- An ECG will be performed (Section 5.2.3).
- Obtain vital signs (pulse rate and blood pressure) (Section 5.2.4).
- A targeted physical examination including weight (Section 5.2.2).
- Subjects will be instructed to return in 7 (\pm 1) days after the last administration of IP for the End of Study visit.

